Cochlear implantation has been reported as a viable treatment option in cases of unilateral hearing loss, including sudden sensorineural hearing loss (Firszt et al, 2012), and severe tinnitus (Vermiere & Van de Heyning, 2009; Van de Heyning et al, 2008). Further, cochlear implantation has been shown to offer superior speech perception in noise, localization abilities, and subjective report in SSD cases as compared to CROS hearing aids and bone-conduction devices (Arndt et al, 2011). The limitation to this comparison, however, was the subjects had limited listening experience with the alternative treatment options (i.e. CROS hearing aids or bone-conduction device). Though other studies reported no difference in abilities with these technologies after 4 weeks of listening experience (Bosman et al, 2003), long-term duration of listening experience may influence speech perception and localization abilities. Considering this, a control condition of long-term users of current treatment options (i.e. bone-conduction devices) may provide a more accurate comparison with SSD cochlear implant recipients.

The primary goal of this project is to determine whether subjects with SSD experience an improvement in speech perception, localization, and quality of life with a cochlear implant as compared to an unaided listening condition. Secondary aims include: 1) a comparison of speech perception, localization, and quality of life outcomes in the study population to a SSD control group with long-term listening experience with a current treatment option (i.e. bone-conduction device), and 2) a within-subject comparison of speech perception and localization abilities with cochlear implantation versus the bone-conduction test device.

III. Objectives

- A. The primary purpose of this feasibility study is to demonstrate the effectiveness of cochlear implantation in subjects with SSD
 - 1. Postoperative results will be evaluated with speech perception measures, localization tasks, and subjective reports

- B. Compare outcomes of cochlear implantation to that of current treatment options (i.e. bone-conduction devices) for SSD cases
 - 1. Compare speech perception, localization, and subjective outcomes to a control group of implantable bone-conduction device recipients
 - 2. Assess cochlear implant subjects with a bone-conduction test device and/or previous BAHA device at the preoperative and 12 month follow-up intervals

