 - 1. Subjects will participate in two aural rehabilitation sessions with a board-certified speech-language pathologist. One session will be after the initial activation of the external speech processor. This will occur either on the same day as the initial activation or within the first 2 weeks of listening experience. The second session will be scheduled in conjunction with the 1-month post-initial activation interval.

VIII. Proposed Claims

- A. Demonstrate the effectiveness of cochlear implantation in SSD subjects
 - 1. Demonstrate an improvement in speech perception abilities, localization, and/or subjective benefit in an aided (cochlear implant on) versus an unaided (cochlear implant off) condition
- B. Cochlear implantation provides similar or superior speech perception, localization, and/or quality of life as compared to that found with bone-conduction devices
 - 1. Comparison with control group performance
 - 2. Comparison within subject when listening with bone-conduction test device

IX. Statistical Analysis

- A. Descriptive summaries will be provided for the following: subject demographics, and frequency of major and minor complications/adverse events.
- B. A single-subject design will be utilized, where each subject serves as his or her own control, for analysis of objective and subjective results. A single-subject design was chosen in order to accommodate the heterogeneity that is well known to characterize auditory prosthesis research. Repeated-measures ANOVA will be calculated with a p-value of ≤ 0.05 for statistical significance. Statistical analysis will be conducted with SPSS software.
 - 1. Comparison of aided speech perception performance on word and sentence materials in the post-initial activation intervals to evaluate trends over time

- a. Comparison of the difference between the aided and unaided conditions at each follow-up interval
- 2. Comparison of localization abilities in the post-initial activation intervals
 - a. Comparison of the difference between the aided and unaided conditions for each follow-up interval
 - b. Compute the overall rms error, random error, constant error, and adjusted constant error, as described by Grantham et al (2007)
- 3. Comparison of subjective report scores in the post-initial activation intervals

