- C. The incidence of interference between ears will be assessed by comparing the speech perception performance in the 0° azimuth conditions for the contralateral ear only versus cochlear implant + contralateral ear conditions for each subject, as well as the individual's subjective report.

A sample size for the cochlear implant recipient cohort of 20 subjects was selected due to known variability in conventional cochlear implant recipient outcomes and to allow for possible dropouts (approximately 20%). A comparable study, Hansen, Gantz & Dunn (2013) evaluated 29 cochlear implant subjects with SSD, which included etiologies of sudden sensorineural hearing loss, Meniere's disease, and vestibular schwannoma. Authors reported a high degree of variability in their sample. This project will not enroll all of the etiologies included in the Hansen, Gantz & Dunn (2013) analysis (such as, Meniere's Disease with intractable vertigo or history of vestibular schwannoma), therefore a smaller sample size was selected. The inclusion/exclusion criteria associated with this study, as compared to the heterogeneity of the Hansen, Gantz, & Dunn (2013) subject sample, will allow for more generalized comments about subjective and objective outcomes of cochlear implantation in cases of SSD.

If needed, statistical consultation will be sought from the North Carolina Translational and Clinical Sciences Institute (TraCS) or UNC Odum Institute.

X. Endpoints

- A. Safety endpoint
 - 1. The primary safety endpoint is the evaluation of Adverse Events. All Adverse Events will be reported to the UNC IRB. If the UNC IRB or study investigators deem an Adverse Event unacceptable, then this would result in termination of the study.
- B. Primary effectiveness endpoint
 - 1. The primary effectiveness endpoint is the comparison of speech perception, localization abilities and/or subjective report when the cochlear implant is on versus off.
- XI. Risk Analysis

A. Potential risks

The following are risks associated with the MED-EL Concert implant, which is also included in the device description:

- 1. Loss of residual hearing
- 2. Increased vertigo
- 3. Delay of healing of the scar
- 4. Impairment of the sense of taste
- 5. Potential for swallowing difficulties
- 6. Numbness
- 7. Increased tinnitus
- 8. Stimulation of the facial nerve
- 9. Temporary pain and uncomfortable sounds during stimulation

The following are potential risks the subject may experience related to the study procedure:

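### The primary effectiveness endpoint joins three domains by and/or, with no primary measure, visit or decision rule, so on the any-domain reading it permits the 0.05 level does not hold; its on-versus-off contrast cannot be applied to the questionnaires.

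*Combined protocol and SAP*

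**What the plan says.** The objective in III.A reads: "The primary purpose of this feasibility study is to demonstrate the effectiveness of cochlear implantation in subjects with SSD". The claim attached to it in VIII.A.1 is: "Demonstrate an improvement in speech perception abilities, localization, and/or subjective benefit in an aided (cochlear implant on) versus an unaided (cochlear implant off) condition". X.B.1 carries the same *and/or* into the primary effectiveness endpoint: "The primary effectiveness endpoint is the comparison of speech perception, localization abilities and/or subjective report when the cochlear implant is on versus off". The primary-goal paragraph just before III. Objectives instead joins the domains by *and*: "improvement in speech perception, localization, and quality of life with a cochlear implant as compared to an unaided listening condition".

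On analysis, IX.B says "Repeated-measures ANOVA will be calculated with a p-value of ≤ 0.05 for statistical significance" and describes a design in which "each subject serves as his or her own control, for analysis of objective and subjective results". For speech, IX.B.1.a lists "Comparison of the difference between the aided and unaided conditions at each follow-up interval"; IX.B.2.a does the same for localization. For questionnaires, IX.B.3 lists only "Comparison of subjective report scores in the post-initial activation intervals".

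VI.C.1.a and VII.C.4.g name 12 months after activation as the study endpoint. X.B.1 gives no time point.

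**The concern.** The documents do not say how many domains must improve, which score represents a domain, or which visit counts. If one domain is enough, the result that supports the effectiveness claim can be picked after the data are seen, and a per-test threshold of 0.05 no longer limits the chance of a false claim.

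The choice within domains is wide. VII.D.3.b gives eight on/off speech contrasts: CNC and AzBio in quiet, plus AzBio and BKB-SIN in three noise configurations. The AzBio rule can also change the signal-to-noise ratio between subjects, without saying which ratio is compared. IX.B.2.b lists four localization scores. VII.D.4 lists three questionnaires.

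The subjective domain has a further problem. Processor-on and processor-off conditions are defined for speech and localization only, so one of the three components of the primary endpoint has no data in the form that X.B.1 requires.

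**Working it through.** **The plan's own figure.** The only stated level is p ≤ 0.05 per analysis. With one test (k = 1) it gives 0.05, or 0.025 in the implant's favour if the test is two-sided. IX.B does not state sidedness; two-sided is assumed. No familywise level or power is stated.

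**Counts, 12 months only**
- k = 2: one speech and one localization measure.
- k = 3: one measure per domain, supposing that the questionnaire contrast were defined.
- k = 5: four speech contrasts in separated noise (AzBio and BKB-SIN, noise to either side) plus one localization score. This is the narrower reading: IX.C uses the 0° comparison for interference, and XII.A places the expected speech benefit in noise.
- k = 9: all eight speech contrasts plus one localization score.

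The counts use one of the four localization scores and no earlier visits; k = 5 and k = 9 leave out the questionnaires.

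**Method.** Each on/off comparison is treated as a separate paired contrast. For two conditions at one visit, the repeated-measures F test equals the squared paired t.
- Independent tests: 1 − 0.95^k for any p ≤ 0.05, and 1 − 0.975^k for a favourable one.
- Common correlation ρ: 1 − ∫φ(u)[Φ((1.96 − √ρ·u)/√(1−ρ)) − Φ((−1.96 − √ρ·u)/√(1−ρ))]^k du. Drop the second Φ for favourable results only.
- The documents give no ρ; 0 to 0.7 is assumed.

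| k | Any p ≤ 0.05, ρ = 0 | ρ = 0.7 | Favourable, ρ = 0 | ρ = 0.7 |
|---|---|---|---|---|
| 2 | 1 − 0.95² = 0.0975 | 0.083 | 1 − 0.975² = 0.049 | 0.042 |
| 3 | 1 − 0.95³ = 0.143 | 0.109 | 1 − 0.975³ = 0.073 | 0.055 |
| 5 | 1 − 0.95⁵ = 0.226 | 0.148 | 1 − 0.975⁵ = 0.119 | 0.074 |
| 9 | 1 − 0.95⁹ = 0.370 | 0.202 | 1 − 0.975⁹ = 0.204 | 0.101 |

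The first pair of columns is compared with 0.05 and the second pair with 0.025. Simulated paired t tests with n = 16 agree: favourable rates for ρ = 0 and 0.7 are 0.117 and 0.077 at k = 5, and 0.207 and 0.106 at k = 9.

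**Power under an adjusted rule.** The evaluable number is 20 × (1 − 0.20) = 16, from the sample-size paragraph of IX. First-step power is P(T > t) for noncentral t with 15 degrees of freedom and noncentrality d√16 = 4d. Critical values are 2.131 at 0.05, 2.490 at 0.025 and 2.694 at 0.0167. The documents give no effect size, so three values of d are shown.

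| d (SD) | Single test, 0.05 | Holm first step, 2 measures | Holm first step, 3 measures |
|---|---|---|---|
| 0.8 | 85% | 75% | 69% |
| 0.6 | 61% | 48% | 41% |
| 0.5 | 46% | 34% | 28% |

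With two measures having equal true effects, simulated Holm power for at least one is 89-91% at 0.8 SD and 50-53% at 0.5 SD (ρ = 0.5 and 0.3).

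**The case against.** The strongest reply is that the goal paragraph says *and*. If all three domains had to improve, error would not inflate across domains. With one measure each and independent null effects, the favourable joint error is 0.025³, about 0.002%; if only one domain were null, it would be at most 2.5%. This stands, so a reader should not infer that the error rate is exceeded on every reading. But the plan does not adopt that rule, and X.B.1 and VIII.A.1 permit the opposite. Measure and visit would still be open within each domain.

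A reader might also multiply every listed score by every visit: 15 scores at five intervals is 75 tests, and 97.9% if independent. The documents do not support that figure as the trial's error rate. IX.B plans repeated-measures ANOVA, including trends over time, and does not commit to a separate test per score and visit. The k = 5 and k = 9 counts are likewise constructions from the test battery, not planned test lists.

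Third, this is called a feasibility study, with 20 implanted subjects as their own controls, and X.B.1 describes a comparison rather than a pass/fail criterion. That lowers the consequence. It does not remove the need for a rule, because the sentence that says feasibility also makes demonstrating effectiveness the primary purpose.

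Finally, the subjective domain is not beyond analysis. Questionnaires are scheduled preoperatively and at 12 months (VII.D, Appendix A), the own-control wording fits a before-after comparison, and XII.C expects benefit relative to preoperative performance. That comparison is feasible; it is simply not written as the analysis.

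**Conclusion.** The point holds for the any-domain reading. There, even one speech and one localization measure nearly double the single-test error, and the larger part of the inflation comes from the open choice of measures within domains. The size depends on the assumed correlations and on treating the plan as separate 12-month contrasts; adding localization scores or earlier visits would raise it.

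It would be too strong to say that the documents have no time point: they name 12 months, but neither the effectiveness endpoint nor its analysis uses it. The mismatch between the on/off endpoint and the questionnaires stands whatever view is taken of multiplicity.

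Given the feasibility label, this can be rated as something that should be fixed rather than as a bar to proceeding. The stated aim of demonstrating effectiveness still makes a decision rule necessary.

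**What to change.** In VIII.A, IX.B and X.B.1:

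1. Set the primary on/off comparison at 12 months.
2. Before on/off results are examined, or with disclosure if some have been seen, name one speech-in-noise measure and configuration and one localization score, chosen by the sponsor. If AzBio is used, say which signal-to-noise ratio is compared.
3. Replace *and/or* by an explicit rule: at least one of the named measures after Holm adjustment at 0.05, or a stated fixed testing order.
4. In X.B.1, VIII.A.1 and IX.B.3, define the subjective comparison as 12 months against preoperative. State whether it is a third measure in the Holm family or supportive evidence, and align the primary-goal paragraph with that choice. This is the sponsor's decision: making it supportive narrows the stated goal, and a gain seen only on questionnaires could then no longer carry the claim.
5. Report all other measures and visits as secondary, with estimates and 95% confidence intervals.

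No new data are needed. The cost is power per measure: at the Holm first step with two measures and 16 evaluable subjects, about 10 to 13 percentage points over effects of 0.5 to 0.8 SD, and more with three. A fixed order avoids the loss for the first measure only; the second can be claimed only if the first succeeds.

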- k. Tinnitus as the primary purpose for seeking cochlear implantation
- 1. Subject obtains a severe or catastrophic score on the Tinnitus Handicap Inventory (Newman, Jacobson & Spitzer, 1996).
- 3. Enrollment
 - a. This study seeks to enroll twenty (20) subjects
- B. Participants: Control group

Subjects must meet the following inclusion criteria and not exhibit any of the exclusion criteria.

- 1. Inclusion Criteria
 - a. Unilateral moderate-to-profound sensorineural hearing loss
 - i. Unaided residual hearing thresholds from 250-8000 Hz (PTA ≥70 dB HL on the implanted side)
 - ii. Normal to mild residual hearing thresholds from 250-8000 Hz in the contralateral ear ≤35 dB HL at each frequency, 250-8000 Hz
 - b. Recipient of bone-conduction device on affected side
 - i. Recipient of the Bone-Anchored Hearing Aid (BAHA)
 - a. Either the Cochlear BAHA Connect or Attract system
 - ii. At least 12 months of listening experience with the BAHA system
 - c. Greater than or equal to 18 years of age
 - d. Duration of moderate-to-profound sensorineural hearing loss less than or equal to 5 years at time of implantation with bone-conduction device (BAHA)
 - i. Either reported by the subject or documented in previous audiograms
 - e. Willingness to participate in test battery
- 2. Exclusion Criteria
 - a. Non-native English speaker

- i. Speech perception materials are presented in English
- b. Conductive hearing loss in either ear
- c. Compromised auditory nerve, including those with a history of vestibular schwannoma
- d. Inability to participate in test battery
- 3. Enrollment
 - a. This study seeks to enroll at least 10 subjects in the control group
- C. Timeline

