- 1. Surgical
 - a. Facial nerve injury
 - i. Facial nerve monitoring is conducted during the surgical procedure
 - b. Infection
 - i. All subjects will be counseled regarding bacterial meningitis and recommended vaccinations
 - c. Bleeding
 - d. Cerebrospinal fluid (CSF) leak
 - e. Pain
 - f. Scarring

2. Postoperative

- a. Swelling around the incision and/or coil site
- b. Pain

i.

- c. Reduced or loss of pinna sensitivity on the surgical side
 - Typically resolves 1-2 months postoperatively
- d. The cochlear implant may not provide any auditory stimulation
- e. The cochlear implant may provide auditory stimulation, but with a sound quality too poor to aid in the perception of speech
- f. The cochlear implant may provide auditory stimulation, but with a sound quality too poor to aid in localization
- g. Pain associated with the coil and/or placement of the external speech processor on the subject's ear
- h. Movement of the internal receiver
- i. Discomfort from electric stimulation
- j. Facial nerve stimulation
- k. Headache

- 1. Dizziness
- m. Altered taste (i.e. reports of metallic tastes on the same side of the tongue as the surgical ear)
- n. Fatigue during follow-up assessment (completion of the test battery and/or mapping)
- o. The internal device may fail, requiring revision cochlear implantation
- p. The sound from the cochlear implant may interfere with the better hearing ear.
- B. Risk Mitigation
 - 1. Current hearing device options, including CROS hearing aids and bone-conduction devices, would still be available to the subject in the future if the subject does not benefit from the cochlear implant or elects to no longer use the cochlear implant.
 - a. The test battery includes a listening condition to assess the monaural performance of the contralateral ear. Interference of the cochlear implant on the performance of the contralateral ear can be evaluated by comparing the contralateral ear only condition to the cochlear implant + contralateral ear conditions when tested at 0° azimuth, as well as, review the subjective benefit via the subjective questionnaires. If interference is found to impact speech perception and subjective benefit, the subject may elect to discontinue use of the cochlear implant and would still have access to currently approved technologies for SSD.
 - 2. Magnet strength will be assessed at each interval to ensure comfort at the coil site.

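### The plan does not say how subjects whose implant fails, who stop using it or who withdraw enter the primary on/off comparison; a complete-case analysis would probably overstate benefit if leaving is related to poor benefit.

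*Combined protocol and SAP*

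**What the plan says.** **Endpoint.** X.B.1: "The primary effectiveness endpoint is the comparison of speech perception, localization abilities and/or subjective report when the cochlear implant is on versus off".

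**Analysis.** IX.B treats each subject as his or her own control and states "Repeated-measures ANOVA will be calculated with a p-value of ≤ 0.05 for statistical significance". For speech, IX.B.1.a calls for "Comparison of the difference between the aided and unaided conditions at each follow-up interval"; IX.B.2.a does the same for localization. Sidedness is not stated.

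**Sample size.** VII.A.3.a: "This study seeks to enroll twenty (20) subjects". The rationale in Section IX says that this allows for roughly 20% dropout.

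**Events that the protocol foresees.**
- XI.A, postoperative item d: "The cochlear implant may not provide any auditory stimulation".
- XI.A, postoperative item o: "The internal device may fail, requiring revision cochlear implantation". XIII.A.3.b classes revision as a serious anticipated adverse event.
- XI.B.1.a: "If interference is found to impact speech perception and subjective benefit, the subject may elect to discontinue use of the cochlear implant".
- XIV.B: a subject may withdraw at any time, and the investigator may also withdraw a subject.

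**Testing.** VII.D makes the battery due at 1, 3, 6, 9 and 12 months. The implant-on condition is tested with the other ear open (VII.D.3.b.iii and VII.D.3.c.iv).

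Neither Section IX nor Section X defines an analysis population or a missing-data method. Neither says how failure, non-use, revision or withdrawal enters the on/off comparison.

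**The concern.** The speech and localization parts of the endpoint need an on score and an off score from the same subject at the same visit. A subject who has withdrawn, has had the implant removed or declines testing has no on score. A subject awaiting revision, or one who has stopped using the implant, may have none, because no rule says that testing continues.

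These reasons can be related to the outcome: some subjects would leave because the implant gave nothing or made listening worse. The claim in VIII.A is that implantation is effective in SSD subjects, not that it is effective in those who still use it. Repeated-measures ANOVA in its classical form needs complete data across visits. A subject with an unfavourable pair at 3 months and nothing afterwards would therefore lose that pair too. With 20 subjects, one or two such losses can move the headline mean.

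**Working it through.** **1. The plan's own figure.** No effect size, SD, power or sidedness is given, so the sample size of 20 cannot be reproduced. The dropout arithmetic is consistent: 20 × (1 − 0.20) = 16, and 16 / (1 − 0.20) = 20. This is circular, because 16 is not stated. For a two-sided paired t test at 0.05 with 80% power, the detectable standardized difference is 0.66 with 20 subjects and 0.75 with 16.

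**2. Inputs not in the documents.** The number k of implanted subjects without an on score is assumed to be 1 to 4; 4 would fill the whole dropout allowance. Their true on-minus-off difference is taken as r times the mean of the scored subjects.

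**3. Overstatement of the mean.** All-implanted mean / scored-only mean = ((20 − k) + k·r) / 20. The overstatement is the inverse of this, minus 1.

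| k | r = 1 (leaving unrelated to benefit) | r = 0 (no benefit) | r = −0.5 (worse with implant on) |
|---|---|---|---|
| 1 | 0% | 20/19: 5.3% | 20/18.5: 8.1% |
| 2 | 0% | 20/18: 11.1% | 20/17: 17.6% |
| 3 | 0% | 20/17: 17.6% | 20/15.5: 29.0% |
| 4 | 0% | 20/16: 25.0% | 20/14: 42.9% |

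**4. False claims of benefit when the true mean is zero.** Simulation: 40,000 trials, N = 20, differences with SD 1, one-sample t test, nominal 2.5% in the direction of benefit. The k subjects lowest on a score correlated ρ with the true difference are dropped entirely.
- ρ = 0: about 2.5% (nominal).
- ρ = 0.25: 3.4% (k = 1) and 4.0% (k = 2).
- ρ = 0.5: 4.4% (k = 1), 6.0% (k = 2) and 10.4% (k = 4).
- ρ = 1.0: 15.3% (k = 2) and 37.8% (k = 4). Here exactly the worst subjects leave, so these are upper bounds.
- All pairs kept: about 2.5%, whatever ρ is.

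This models one contrast with no usable score from leavers. That is what complete-case ANOVA produces, even when early pairs exist.

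**5. Cost in power of scoring non-working implants as 0.** Take 16 users with a mean of 0.8 SD and 4 true zeros. Simulated power is 84.7% when the four are dropped and 84.4% when they are scored 0, while the mean falls from 0.80 to 16 × 0.80 / 20 = 0.64. A noncentral-t approximation puts the loss somewhat higher: 80.1% versus 77.0% at 0.75 SD. Either way, the estimate changes much more than the power.

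**The case against.** The strongest reply is that most of these subjects can still be scored.
- A silent implant can be tested with the processor on and the other ear open, where on should be about equal to off.
- Interference is detected by comparing the on and off conditions (IX.C and XI.B.1.a), so at least one pair already exists.
- Stopping use is not withdrawal. XI.B.1.a does not say that testing ends, and VII.D exempts nobody from the battery.
- IX.C reports interference for each subject and IX.A reports complications, so failures would be visible beside the effectiveness result.

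All of this stands. A reader might infer that these subjects have no on score, that the primary result describes only successful users, or that the bias always favours the implant. The documents support none of these readings. Poor performers who attend stay in. Only withdrawal, removal without replacement or refusal of testing necessarily loses the score. A hardware failure unrelated to benefit gives no bias, and failure in a good performer would bias the other way. Nor do the documents say that the 20% allowance consists of implant failures.

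The reply does not close the gap. A visit schedule is not a rule for a missing score, and reporting an event as a safety or interference finding does not define its place in the effectiveness estimate. An existing pair helps only if the analysis keeps it, and classical repeated-measures ANOVA does not when later visits are missing.

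**Conclusion.** The concern holds as a gap in the primary analysis with a likely, not certain, direction of bias. The events are foreseen, the handling is not stated, and the named method in its classical form discards partial data.

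The overstatement of mean benefit is 5% to 25% for 1 to 4 unscored subjects with zero true benefit. It is larger if they do worse with the implant on, and nil if missingness is unrelated to benefit. Under a true mean of zero, a false-claim rate of about 4% to 10% goes with a moderate link between leaving and benefit (correlation 0.5). The figure near 38% is an upper bound and should not be read as an expectation. All of these sizes depend on event counts and correlations that the documents do not give.

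The sponsor should fix this before analysis. In a feasibility study of 20 subjects it does not undermine the design.

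**What to change.** Add to IX.B:
1. The on/off effectiveness analysis includes every implanted subject.
2. Subjects who stop using a working implant are still offered the on/off test at the visits already scheduled in VII.D. This concerns assessment only and leaves the choice to stop untouched.
3. If the implant is in place but not working at a visit, the open-ear on-minus-off difference is scored 0. The rule applies only to the open-ear speech and localization comparisons.
4. Visits after revision are kept and flagged.
5. A mixed model that keeps all observed pairs replaces complete-case ANOVA. A mixed model alone would project later benefit for leavers from those who remain. For subjects who withdraw, have the implant removed or decline testing, therefore add sensitivity analyses: last observed pair, and difference 0 or worst case. The last pair should not be the main rule, because it may freeze an early score while the protocol's background section expects growth up to 6 to 12 months.
6. The users-only result is secondary, and the number on each path is given out of all implanted.

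Cost: a few sentences and a little more analysis work, with no new visits or tests. The estimate is likely to become slightly less favourable; the power cost of item 3 is small.
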